**\* \* \* Personnel Information \* \* \***

Starred items indicate required fields whenever that section is completed.

**Is this a student led research?\***

N

**ALL research personnel are required to complete Human Subject Research training.**

**Which human subjects research training was completed for this protocol?\*** CITI

See memo regarding appropriate human subjects training.

The Research Compliance Office will verify the last date of completion below.

Attach file of NIH training certificate in Attachments Section.

NIH Completion Date	
Training Details	
No training data is available.	

### Subject Checklist

#### Select All That Apply :

Children and/or students under 18 years of age (including neonates)

Pregnant women/ fetuses

Prisoners

Military personnel

Adult Volunteers

Economically/educationally disadvantaged

Mentally ill

University students

University employees

Illiterate

Homeless

Public officials/candidates for public office

Institutionalized patients/residents

Persons incompetent to give consent (e.g., dementia, comatose, have legal guardians)

Healthy Individuals

Other (please specify):

---

### \* \* \* Study Location \* \* \*

### Study Location

Select All That Apply - NOTE: Check "Other" and input text: 1.) If your study location is not listed, or 2.) If you would like to list details of your already-checked location (e.g., specific school within a school district)

University of Hawaii, Manoa

University of Hawaii, Hilo

University of Hawaii, West Oahu

University of Hawaii Community Colleges

School/School District

Hawaii Public School

Hawaii Charter School

Private school

Medical Health Care Facility

Queens Medical Center (QMC)

Hawaii Pacific Health (HPH)

Castle Medical Center

**Protocol Title:** Buffered Lidocaine for Paracervical Block to Decrease Injection Pain During First Trimester Surgical Abortions

**Protocol Type:** Unified IRB Form

**Date Submitted:** 01/30/2017

**Approval Period:** Draft

**Important Note:** This Print View may not reflect all comments and contingencies for approval. Please check the comments section of the online protocol. Questions that appear to not have been answered may not have been required for this submission. Please see the system application for more details.

---

Shriners Hospitals for Children - Honolulu

Other (please specify)

Women's Options Center - faculty practice sites

Has this protocol or proposal been or will it be submitted to any Institutional Review Board(s) or ethics review committees other than the UH IRB?  N

Is this a multi-site project? (A multi-site study is one where different PIs at different institutions are conducting the same study or aspects of the same study.)  N

If this study also involves site(s) outside UH, will UH function as the coordinating center or lead institution? (Check N/A for studies done solely at UH.)

Yes

No

N/A

Please attach any and all non-UH IRB approval correspondence or letters of permission / support from external study sites, if applicable, in the Attachment section.

---

#### \* \* \* General Checklist \* \* \*

#### General Checklist

Select All That Apply, unless otherwise indicated :

**Section 1: If you are requesting that UH cede IRB authority to another IRB, stop here, do not use this application. Instead, submit the following materials to the Human Studies Program Office at [[contact]](mailto:[contact]).**

Request to have UH IRB be the Relying IRB: In addition to completing the application, please also include in the Attachment section the following required materials: (1) Memorandum requesting to designate UH IRB as the relying IRB with justification (2) IRB Authorization Agreement signed by the other institution's Institutional Official (template can be found by clicking the HELP button in the top right corner of this page).

#### Section 2: Biomedical Research

Industry-Sponsored Clinical Trial

Human blood, cells, tissues, or body fluids (Institutional BioSafety)

Tissues to be stored for future research projects

Tissues to be sent out of this institution as part of a research agreement (Material Transfer Agreement (MTA))

Human Embryos

Human Embryonic Cells? Provide NIH Code Number(s) or state that no federal funding will be used to support this research.

Use of Patient related equipment? If Yes, specify what equipment is being used.

Radioisotopes/radiation-producing machines, even if standard of care (Radiation Safety)

Investigational Device

This study involves drugs or devices regulated by FDA

Cancer Subjects (e.g., clinical trials, behavior/prevention) or Cancer Tissues (e.g., blood, cells, body fluids).

Investigational drugs, reagents, or chemicals

Commercially available drugs, reagents, or other chemicals administered to subjects (even if they are not being studied)

#### Section 3: Methodologies

Interview

**Protocol Title:** Buffered Lidocaine for Paracervical Block to Decrease Injection Pain During First Trimester Surgical Abortions

**Protocol Type:** Unified IRB Form

**Date Submitted:** 01/30/2017

**Approval Period:** Draft

**Important Note:** This Print View may not reflect all comments and contingencies for approval. Please check the comments section of the online protocol. Questions that appear to not have been answered may not have been required for this submission. Please see the system application for more details.

---

Questionnaire/Survey  
Blood Draw

#### Section 4: For Student-led research

Thesis or Dissertation Project (Please upload proposal and dissertation/thesis committee approval (if available) in Attachments section.)  
Class Project

#### Section 5: Other

This study is or will be posted on ClinicalTrials.gov  
If checked, specify the number in the field to the right: TBD

Protocol involves studying potentially addicting drugs.

Protected Health Information (PHI) will be viewed, created, accessed, used, or disclosed.

HIPAA Authorization

Waiver or Alteration of Authorization

Activities Preparatory to Research

Limited Data Set and Data Use Agreement

Use and Disclosure of Decedents PHI without Authorization

Specify any other (use the text box to the right)

---

#### \* \* \* Funding \* \* \*

NONE--This project does not have any funding. If you want to add Funding for the study, please uncheck "NONE."

#### Funding

Add external and internal grant funding source(s) below: Federal Government, Other Gov. (i.e., State, local), Foundation or Other. Select "None" above if there is no external funding for the study.

Funding for this study has been secured by the UH Office of Research Services (ORS)

---

#### \* \* \* Application Type Checklist \* \* \*

#### Application type checklist

Not Human Subjects Research/Undefined Research/Training or Infrastructure Grant

Exempt

Expedited/Full Board

**Protocol Title:** Buffered Lidocaine for Paracervical Block to Decrease Injection Pain During First Trimester Surgical Abortions

**Protocol Type:** Unified IRB Form

**Date Submitted:** 01/30/2017

**Approval Period:** Draft

**Important Note:** This Print View may not reflect all comments and contingencies for approval. Please check the comments section of the online protocol. Questions that appear to not have been answered may not have been required for this submission. Please see the system application for more details.

---

**\* \* \* Expedited Paragraphs \* \* \***

**PLEASE READ:** For Expedited Review, all aspects of the research must include activities that (1) present no more than minimal risk to human subjects, and (2) involve one or more of the specific categories listed below.

Select the following applicable categories to determine if your research project qualifies under Expedited Review. If none of the categories are applicable to your research project, a Full Committee Review will be required. For Expedited or Full Review, proceed to complete the following application. If none of the expedited criteria are appropriate for your project, please move to the next screen WITHOUT checking any of these criteria; your protocol will be reviewed by the full IRB. Note: The IRB will make the final determination if your protocol is eligible for expedited review.

Select one or more of the following paragraph(s):

Check all that apply	Category	Description
	1.	Clinical studies of drugs and medical devices when an IND or IDE application is not required by the FDA.
	2a.	Collection of blood samples by finger stick, heel stick, ear stick or venipuncture from healthy, non-pregnant adults who weigh at least 110 pounds.
	2b.	Collection of blood samples by finger stick, heel stick, ear stick or venipuncture from other adults and children, considering the age, weight and health of the participants, the collection procedure, the amount of blood to be collected, and the frequency with which it will be collected.
	3.	Prospective collection of biological specimens for research purposes by non-invasive means.
	4.	Collection of data through non-invasive procedures, not involving general anesthesia or sedation, routinely employed in clinical practice, excluding procedures involving x-rays or microwaves.
	5.	Research involving materials, such as data, documents, records, or specimens, that have been collected or will be collected solely for non-research purposes, such as medical treatment or diagnosis.
	6.	Collection of data from voice, video, digital, or image recordings made for research purposes.
	7a.	Research on individual or group characteristics or behavior, including but not limited to research on perception, cognition, motivation, identity, language, communication, cultural beliefs or practices, and social behavior.
	7b.	Research employing survey, interview, oral history, focus group, program evaluation, human factors evaluation, or quality assurance.

---

**\* \* \* Summary, Purpose, Procedures \* \* \***

**Title (Please indicate if the protocol title is different from the proposal title)**

Buffered Lidocaine for Paracervical Block to Decrease Injection Pain During First Trimester Surgical Abortions

**Proposed Start Date:**

02/01/2017

**Proposed End Date:**

06/30/2019

**Protocol Title:** Buffered Lidocaine for Paracervical Block to Decrease Injection Pain During First Trimester Surgical Abortions

**Protocol Type:** Unified IRB Form

**Date Submitted:** 01/30/2017

**Approval Period:** Draft

**Important Note:** This Print View may not reflect all comments and contingencies for approval. Please check the comments section of the online protocol. Questions that appear to not have been answered may not have been required for this submission. Please see the system application for more details.

## 1. Summary

a) Provide a brief summary of the scope of work of this project, using non-technical terms that would be understood by a non-scientific reader. This summary should be no more than 200 words.

First trimester surgical abortions are one of the most common outpatient procedures worldwide. Approximately 42 million are performed annually. Many different techniques have been used for pain control during this procedure. Some providers use conscious sedation, general anesthesia, or listening to music. Most providers use the paracervical block, a numbing injection into the cervix, either alone or in combination with other pain control techniques. The paracervical block has been shown to decrease pain during the procedure especially at earlier gestations. Some studies have shown a decrease in pain with four site injection paracervical blocks rather than the conventional two site injection. Some providers believe that a waiting period after the paracervical injection decreases pain. Some providers use buffered lidocaine due to a belief that it decreases pain. Others use plain lidocaine. At our clinics, the standard pain management protocol is using 20 cc of 1% plain lidocaine in a two site injection. Few studies have compared buffered versus nonbuffered lidocaine for paracervical blocks during first trimester surgical abortions. This study seeks to determine if buffered lidocaine decreases injection pain versus plain lidocaine for paracervical blocks.

## 2. Purpose

a) Describe the purpose for the proposed project as well as the hypotheses/research questions to be examined.

The purpose of this study is to see if using buffered lidocaine for the standard paracervical block will decrease the injection pain normally associated with the plain lidocaine solution we use as our standard protocol. Plain lidocaine is commonly used for paracervical blocks. However, some studies have suggested that buffered lidocaine may decrease the pain associated with the injection of the medication, but few studies have looked specifically at using buffered lidocaine for paracervical blocks during first trimester outpatient surgical abortions. Our hypothesis is that using buffered lidocaine for the paracervical block during first trimester surgical abortions will decrease injection pain as compared to using plain lidocaine.

b) What do the investigators hope to learn from this project?

Primary objective: To assess if buffered lidocaine reduces pain from injection more effectively than plain lidocaine for paracervical blocks during first trimester surgical abortions

Secondary objectives: To evaluate if buffered lidocaine is more effective than plain lidocaine at reducing pain during dilation and postoperative pain from first trimester surgical abortions

## 3. Procedures

a) Describe in chronological order of event(s) how the activities will be conducted, providing information about all procedures (e.g. interventions/interactions with subjects, data collection, photographing, audio and video recording), including follow up procedures.

Potential participants will be identified at their office visits to the University Women's Health Specialists either at Kapi'olani or Queen's. If a patient desires surgical termination of a first trimester pregnancy or management of a failed pregnancy in the first trimester, they will first receive standard counseling and provide informed consent for the procedure. Next, the patient's eligibility for our study will be assessed. If the patient is eligible, she will be asked by a member of the research team if she is interested in participating. If she is, the study will be explained to her and written consent will be obtained after she is given the opportunity to have all of her questions answered. The patient will then complete a written questionnaire to collect demographic data.

This prospective randomized control trial will consist of two study arms. As participants are enrolled they will be randomly assigned to Arm 1, where a paracervical block will be administered with 20 cc of 1% lidocaine, which is our standard office protocol, or to Arm 2, where a paracervical block will be administered with 20 cc of 1% lidocaine buffered with 8.4% sodium bicarbonate. Patients will be randomly assigned to either Arm 1 or Arm 2 of the study. Prior to the start of the study, study assignments will be generated in a 1:1 ratio. A statistician not involved with the conduct of the study will use a computer random number generator to generate random permuted blocks. The random permuted blocks will also be randomly varied in sizes of 4, 6, & 8. This statistician will place allocation assignment cards in sequentially numbered, sealed, opaque envelopes. A different randomization scheme will be used for each location, one at the Kapi'olani office and one at the Queen's office.

A clinic staff member not involved with the conduct of the study will be trained specifically in the opening of the allocation envelopes. The clinic staff member will be trained to pull envelopes individually in a sequentially numbered order. The staff member will be trained to open the envelope and remove the study card to read the allocation group: buffered lidocaine or plain lidocaine. The staff member will be trained to not tell anyone involved in the study of the allocation assignment. The clinic staff member will then draw up the buffered lidocaine or plain lidocaine in an unlabeled syringe, and give it to the procedural physician or surgical assistant for study administration.

**Protocol Title:** Buffered Lidocaine for Paracervical Block to Decrease Injection Pain During First Trimester Surgical Abortions

**Protocol Type:** Unified IRB Form

**Date Submitted:** 01/30/2017

**Approval Period:** Draft

**Important Note:** This Print View may not reflect all comments and contingencies for approval. Please check the comments section of the online protocol. Questions that appear to not have been answered may not have been required for this submission. Please see the system application for more details.

---

All patients who consent to the study will receive standard counseling prior to their procedure. The procedure will start with a bimanual exam by the provider. Next, the provider will place a speculum, cleanse the cervix with betadine solution, and place a single-tooth tenaculum on the anterior lip of the cervix. At this point, participants assigned to Arm 1 will receive a paracervical block loaded with 20 cc of 1% lidocaine with 10 cc injected at the 4 and 8 o'clock positions of the cervicovaginal junction. Participants assigned to Arm 2 will receive a paracervical block loaded with 18 cc of 1% lidocaine and 2 cc of 8.4% sodium bicarbonate in the same fashion. The research assistant will ask the patient to verbally report their level of pain based on the 100 mm visual analog scale at the following points of the procedure:

- 1) Prior to the start of the procedure (baseline)
- 2) After speculum placement
- 3) After paracervical block
- 4) After cervical dilation
- 5) After suction curettage
- 6) Fifteen minutes postoperatively

i) Be sure to identify what procedures are experimental and what are standard of care or established practice for the condition/situation.

Our current standard of care is to use 20 cc of 1% plain lidocaine for the paracervical block. We are experimenting using a paracervical block loaded with 18 cc of 1% lidocaine and 2 cc of 8.4% sodium bicarbonate to see if this decreases injection pain.

b) Explain who will conduct the procedures and where and when they will take place. Indicate the frequency and duration of visits/sessions as well as the subject's total time commitment for the study. Include how the data will be collected (i.e. in person or online).

Abortion care providers will perform the dilation and curettage at University Women's Health Specialists either at the Kapi'olani or Queen's location. The research portion will take place on the same day as the dilation and curettage procedure and will add an additional 20 minutes to the patient's standard office visit. No additional visits are required for this research study. Data will be collected in person and recorded on paper then transferred to a secure electronic database.

i) Indicate that the instruments used are in the public domain or provide appropriate documentation of permission to use each scale.

All instruments used are in the public domain.

c) For school-based activities where class time is used, describe in detail the activities planned for non-subjects and explain where both subjects and nonsubjects will be located during the activities.

N/A

d) State if deception will be used. If so, provide a rationale and describe debriefing procedures. Submit a debriefing script in attachments section

N/A

e) Will audio or video taping of individuals occur? Will photographs of individuals be taken? Describe what will become of the tapes/photographs (e.g., shown at scientific meetings, erased, etc.).

N/A

f) Will the proposed research involve the use of existing data/specimens? If so, check all that apply:

- i. The research involves data from publicly available sources
- ii. That data will be recorded by the investigator in such a manner that subjects cannot be identified.
- iii. Any link to identifying information has been destroyed
- X iv. N/A

**Protocol Title:** Buffered Lidocaine for Paracervical Block to Decrease Injection Pain During First Trimester Surgical Abortions

**Protocol Type:** Unified IRB Form

**Date Submitted:** 01/30/2017

**Approval Period:** Draft

**Important Note:** This Print View may not reflect all comments and contingencies for approval. Please check the comments section of the online protocol. Questions that appear to not have been answered may not have been required for this submission. Please see the system application for more details.

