Based on previous research showing that a clinically relevant decrease in pain on a 100 mm VAS is at least 15 mm, we need to enroll 88 patients (44 in each group) to show this difference with 80% power and alpha of 0.05. Inflating this number by 10% to account for potential dropout (which is unlikely due to the lack of longitudinal follow-up), we obtain a total sample size of 98 patients (49 in each group).

Based on the typical volume of patients seen in our office practice, we anticipate that enrollment will take approximately 6-8 months.

We will assess the primary objective by comparing the mean pain score after paracervical block from participants receiving buffered

**Protocol Title:** Buffered Lidocaine for Paracervical Block to Decrease Injection Pain During First Trimester Surgical Abortions

**Protocol Type:** Unified IRB Form

**Date Submitted:** 01/30/2017

**Approval Period:** Draft

**Important Note:** This Print View may not reflect all comments and contingencies for approval. Please check the comments section of the online protocol. Questions that appear to not have been answered may not have been required for this submission. Please see the system application for more details.

---

We will assess the primary objective by comparing the mean pain score after paracervical block from participants receiving buffered lidocaine versus the mean pain score after paracervical block from participants receiving plain lidocaine. To assess our secondary objectives, we will compare the mean pain score after cervical dilation between participants assigned to Arm 1 and Arm 2 as well as compare postoperative pain between the two arms. All analyses will assume a statistical significance level of 0.05. In addition, we will monitor the extra costs of preparing buffered lidocaine solutions and how the preparation of buffered lidocaine impacts clinic flow and staffing.

c. Alternative Procedures. Describe any alternatives to participating in the research. (e.g., standard of care treatment, etc.). Any standard treatment that is being withheld must be disclosed. This information must be included in the consent form.

If a participant decides to withdraw from the study, she will receive our standard of care which is to administer a paracervical block using 20 cc of 1% plain lidocaine prior to the procedure.

d. Will subjects be followed after their active participation is complete?

N

If yes, explain why and describe how:

---

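### Allocation is stratified by office but the analysis text never mentions office; read as an unadjusted comparison of means, it would be mildly conservative if mean pain differs between the offices

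*Combined protocol and SAP*

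**What the plan says.** On allocation, section 3a (Procedures) states that "study assignments will be generated in a 1:1 ratio", that "The random permuted blocks will also be randomly varied in sizes of 4, 6, & 8", and that "A different randomization scheme will be used for each location", the two locations being the Kapi'olani and Queen's offices. This is randomisation stratified by office with small blocks.

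On analysis, section 4b (statistical methods) says of the primary outcome: "We will assess the primary objective by comparing the mean pain score after paracervical block from participants receiving buffered lidocaine" with the same mean under plain lidocaine. For the secondary outcomes, "we will compare the mean pain score after cervical dilation between participants assigned to Arm 1 and Arm 2", and postoperative pain is compared between arms as well. It adds: "All analyses will assume a statistical significance level of 0.05".

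Section 4b names no test, model, covariate or interval, and does not mention office. It specifies neither an adjusted nor an explicitly unadjusted analysis. Section 16 (Attachments) lists a separate protocol document that was not among the material supplied.

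**The concern.** Separate blocked lists keep the arms nearly balanced within each office. A difference in mean pain between the offices therefore adds almost nothing to the true sampling error of the arm difference. A plain two-sample comparison of means does not use this. Its pooled variance includes the spread between offices, so its standard error is larger than the real one.

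The consequence is lost efficiency. Intervals would be wider than they need be, the test would reject a true null hypothesis less than 5% of the time, and some of the precision bought by stratifying would be given up. The estimate itself stays unbiased.

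There is also a point of prespecification. Because section 4b is silent, whether to include office remains a choice that could be made after the data are seen.

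**Working it through.** **Inputs from the protocol.** Two offices with separate 1:1 lists and blocks of 4, 6 and 8 (section 3a). Target difference 15 mm on a 100 mm VAS, 80% power, alpha 0.05, 44 per arm, and 98 in total after a 10% dropout allowance (section 4b).

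**Inputs that must be assumed.** The SD, the difference in mean pain between offices (d) and the share of patients at one office (p). I also take the test as two-sided, since section 4b does not say.

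**Step 1: the plan's own figure.** No SD is stated, so 44 per arm can only be solved backwards:

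SD = 15 / [(1.960 + 0.842) × √(2/44)] = 15 / (2.802 × 0.2132) = 25.1 mm.

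With the t distribution the answer is 24.8 mm. The dropout step reproduces: 88 / 0.9 = 97.8, rounded up to 98. I use 25 mm as the within-office SD (s) and show 20 and 30 mm as a range.

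**Step 2: formula.** With the arms balanced within office, the arm difference has true variance proportional to s². The unadjusted pooled variance estimates s² + p(1−p)d². The standard error is therefore too large by the factor

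R = √(1 + p(1−p)d²/s²),

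and the type I error is about 2[1 − Φ(1.96R)].

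For an even split and s = 25 mm:

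- d = 10 mm: R = √(1 + 0.25 × 100/625) = √1.04 = 1.020; type I error 0.046.
- d = 20 mm: R = √(1 + 0.25 × 400/625) = √1.16 = 1.077; type I error 0.035.

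**Step 3: simulation.** 40,000 trials per setting, N = 98, separate lists per office with blocks of 4, 6 and 8, normal scores, two-sided 0.05. Even split, s = 25 mm:

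| Office difference (mm) | Mean SE, unadjusted | Mean SE, with office | Interval too wide by | Type I error, unadjusted |
|---|---|---|---|---|
| 5 | 5.06 | 5.04 | 0.5% | 0.049 |
| 10 | 5.14 | 5.04 | 2.0% | 0.045 |
| 15 | 5.27 | 5.04 | 4.5% | 0.041 |
| 20 | 5.43 | 5.04 | 7.8% | 0.036 |
| 25 | 5.64 | 5.04 | 12.0% | 0.029 |

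With the office term the type I error is 0.048 to 0.051 throughout. With no office difference both standard errors are 5.04. The Monte Carlo error is about 0.001 for type I error and 0.002 for power.

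**Step 4: sensitivity to the assumptions.**

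| Setting | At 10 mm: type I error, excess width | At 20 mm: type I error, excess width |
|---|---|---|
| Split 74:24, SD 25 | 0.047, 1.5% | 0.038, 5.9% |
| Split 88:10, SD 25 | 0.049, 0.7% | 0.044, 2.9% |
| Even split, SD 20 | 0.043, 3.1% | 0.029, 12.0% |
| Even split, SD 30 | 0.047, 1.4% | 0.037, 5.5% |

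**Step 5: power for 15 mm, even split, within-office SD 25 mm.** At N = 98, unadjusted versus with office: 83.7% versus 83.6% (no office difference), 82.1% versus 83.2% (10 mm), 79.5% versus 83.7% (20 mm). At N = 88, 100,000 data sets per setting give unadjusted power of 79.5%, 78.1% and 74.7% at 0, 10 and 20 mm, against about 79.4% to 79.6% with office.

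**The case against.** Four points can fairly be made against this.

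1. **The unadjusted reading is inferred.** Comparing mean scores between arms is compatible with an office-adjusted model, and the wider gap is that no method is named at all. This stands, and it is why the concern is conditional. Silence still leaves the choice open.

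2. **The attached protocol may already deal with it.** This also stands. If that document includes office, the two texts need only be aligned.

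3. **Nothing suggests that the offices differ.** They belong to one practice and share a standard block, procedure sequence, pain-rating method and eligibility criteria. A 15 mm office difference would equal the treatment effect that the protocol calls clinically relevant. At 5 to 10 mm the effect on type I error and interval width is slight, and an uneven split shrinks it further. This limits the importance of the point, not its direction.

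4. **The power figures depend on what 25 mm represents.** It is back-solved from a two-group formula without an office term, so it reads most naturally as the overall SD. If the overall SD is held at 25 mm, the within-office SD is √(625 − 0.25d²), or 24.5 mm at d = 10 and 22.9 mm at d = 20. With 44 per arm, an even split and the normal approximation, unadjusted power is then 80.4%, 80.8% and 82.4% at 0, 10 and 20 mm, against 81.9% (10 mm) and 86.7% (20 mm) with office. On that reading no planned power is lost; an available gain is forgone. This is correct, and the figures in Step 5 should not be taken as erosion of the design's stated power. The excess width and the low type I error remain under either reading: 25/24.5 = 1.02 at 10 mm and 25/22.9 = 1.09 at 20 mm.

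**Conclusion.** The concern holds in its conditional form. Allocation is stratified by office and the supplied analysis text does not use office. Carried out as an unadjusted comparison of means, the analysis would be conservative whenever the offices differ in mean pain. The direction follows from the design; the size depends on an SD, an office difference and an enrolment split that the documents do not give.

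The effect is minor up to about a 10 mm office difference. It becomes noticeable only from roughly 15 mm with a fairly even split. The unadjusted comparison would remain valid, and no conclusion of the trial is endangered. This is an inexpensive improvement that the investigators should consider.

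**What to change.** In section 4b, state that for pain after the paracervical block (primary), pain after dilation and postoperative pain (secondary), the difference in mean pain between arms and its 95% CI will be estimated from a linear model with arm and office as fixed effects. If the attached protocol already says this, bring section 4b into line with it.

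The cost is one sentence and one degree of freedom. Office is known for every participant, the sample size does not change, and no measurable power is lost if the offices turn out not to differ.
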